## 6.4 Analysis Plan Overview

Interim analyses will be performed after approximately 100 and 200 subjects have been randomized and followed through the 4-month follow-up period.

The primary endpoint will be compared between those who are treated with standard of care and access to the PKG (PKG+ Group) and those who are treated per standard of care alone (PKG- Group) via a two-sample t-test. Except where otherwise specified, the following general principles apply to the planned statistical analyses. All statistical analysis will be conducted using SAS version 9.4 or later (SAS Institute Inc., Cary, NC) or other widely-accepted statistical or graphical software as required. Continuous variables will be summarized with mean, standard deviation, median, max, min, and number of evaluable observations. Categorical variables will be summarized with frequency and percentages. Confidence intervals may be presented where appropriate using the t-distribution for continuous variables and Clopper -

Pearson Exact method for categorical variables. Unless otherwise specified, statistical analyses will be performed using a one-sided 0.025 alpha level.

Additional analyses will be conducted to adjust for key baseline characteristics associated with either outcome or group assignment. A subset analysis related to falls per the ancillary endpoint will be performed at selected sites. These analyses will be performed using linear regression with primary predictor of group assignment and outcome of change in Total MDS-UPDRS, and further detailed in the study Statistical Analysis Plan.

## 7.0 Investigator Qualifications

Movement Disorder Specialists and General Neurologists who treat PD participating in this study will be using the PKG in routine clinical care and have completed PKG product training provided by GKC and be trained on the use of target ranges prior to participating in this study.

## 8.0 Risk/Benefit Analysis

All aspects of clinical management will be made at the clinician's discretion and with the patient's safety in mind. This study represents a minimal risk as both groups are undergoing clinician-guided medication management. Furthermore, the PKG Movement Recording System within this study fulfills the following general criteria:

- **Not** intended as an implant or presents a potential for serious risk to the health, safety, or welfare of a subject;
- **Not** purported or represented to be for use in supporting or sustaining human life and presents a potential for serious risk to the health, safety, or welfare of a subject, or
- **Not** for a use of substantial importance in diagnosing, curing, mitigating, or treating disease, or otherwise preventing impairment of human health and presents a potential for serious risk to the health, safety, or welfare of a subject.

In the case of the PKG+ group, additional objective measures will also be used to help guide the clinician. The results of this study are expected to yield generalizable knowledge about the utility of using objective measures in the management of PD.

In this post-market clinical study, study sites and participants will use commercially available system components according to existing product labeling. The study includes non-invasive clinical assessments and patient surveys routinely used to characterize Parkinson's disease symptoms. The study includes study-specific clinician and patient surveys as well.

Adverse events and risks associated with this study are similar to those normally associated with standard clinical care of patients with Parkinson's disease; thus, additional adverse events are not anticipated.

However, only the list below of protocol defined adverse events will be collected starting at point of enrollment and analyzed for the ancillary endpoints:

- falls
- orthostatic hypotension
- bothersome hallucinations
- delirium
- impairment that prohibits interaction with the PKG watch
- hospitalizations
- emergency department visits
- urgent care visits
- unanticipated clinic visits

An independent review of protocol collected adverse and serious adverse events will be performed and assessed related to protocol, study eligibility and outcomes. Events will be reported to IRBs and regulatory authorities as applicable.

Current product safety information, including contraindications, warnings, and precautions, are located in the Patient Instructions Manual, Technical Instructions Manual, and Clinical Interpretation Guide. Any complaints regarding any component of the PKG Movement Recording System will be reported to GKC and processed per GKC's standard post-market surveillance processes and any adverse events associated with the use of the PKG Movement Recording System will be summarized in the final report for this study.

## 9.0 Study Monitoring and Oversight

Trained personnel appointed by GKC will conduct monitoring activities to ensure that the study is conducted in accordance with this study protocol, applicable regulatory requirements and clinical guidelines. Monitoring activities will include a combination of ongoing remote data review, risk-based monitoring and on-site source document verification. No formal Data Safety and Monitoring Committee will be established for this study as this is a minimal safety risk study. However, as previously outlined, the Clinical Trial Steering Committee will periodically review study parameters including interim analyses.

Each center will obtain Institutional Review Board (IRB) approval of this study protocol and informed consent prior to commencement of subject enrollment and remain under the administration of an IRB throughout the duration of the study.

## 10.0 Abbreviations and Definitions

AE	Adverse Event – Any untoward medical occurrence in a participant, which does not necessarily have a causal relationship with the trial intervention.
BKS	Bradykinesia Score – A score produced by PKG algorithms indicating symptoms of bradykinesia
DKS	Dyskinesia Score – A score produced by PKG algorithms indicating symptoms of dyskinesia.
FDS	Fluctuation Dyskinesia Score – A score produced by PKG algorithms indicating levels of fluctuation shown but interquartile ranges.
IQR	Interquartile Range - A measure of statistical dispersion, being equal to the difference between 75th and 25th percentiles.
LED	Levodopa Equivalent Dose – The comparison of levodopa with other medication regimes.
MoCA	Montreal Cognitive Assessment – A rapid screening instrument for mild cognitive dysfunction.
PD	Parkinson’s Disease – A progressive disease of the nervous system marked by tremor, muscular rigidity, and slow, imprecise movement, chiefly affecting middle-aged and elderly people. It is associated with degeneration of the basal ganglia of the brain and a deficiency of the neurotransmitter dopamine.
PDQ-39	Parkinson’s Disease Questionnaire – A 39 self-report questionnaire that assesses Parkinson’s disease-specific health related quality over the previous month.
PKG	Personal KinetiGraph - The output (including graphs, values, and curation) generated from the data captured on the PKG watch
PTI	Percent Time Immobile – Overall percentage of time the PKG detects that the patient is motionless.
PTT	Percent Time Tremor – Overall percentage of time the PKG detects that the patient experiences tremors.
PwP	People with Parkinson’s Disease
Target Ranges	Defined using Pahwa R, Isaacson SH, Torres-Russotto D, Nahab FB, Lynch PM, Kotschet KE. Role of the Personal KinetiGraph in the routine clinical assessment of Parkinson’s disease: Recommendations from an expert panel. Expert Review of Neurotherapeutics. 2018. DOI: 10.1080/14737175.2018.1503948.

	Target Range
Bradykinesia Score (BKS)	Median BKS 23-25 and/or FDS > 7.5

Dyskinesia Score (DKS)	Median DKS 7-9 and FDS < 13
-----------------------------------	-----------------------------

UPDRS-MDS Unified Parkinson's Disease Rating Scale, MDS version – A revision of the universally accepted UPDRS. (Goetz CG et al. Movement Disorder Society-Sponsored Revision of the Unified Parkinson's Disease Rating Scale (MDS-UPDRS): Scale Presentation and Clinimetric Testing Results. Movement Disorders. Vol. 23, No. 15, 2008, pp. 2129-2170.)

Statistical Analysis Plan

Utilization of Target Ranges to Treat Patients with Parkinson's Disease by Objective Measurement Using the Personal KinetiGraph® (PKG®) compared to Standard of Care Assessment (TARGET-PD)- A Randomized Controlled Trial

Global Kinetics Corporation

Effective Date: 09Sep20

Version: 1.0

Approved By:

Printed Name/Title

[name]
Director Clinical Research
Global Kinetics

Signature

A handwritten signature in black ink, appearing to read "[name]", written over a horizontal line.

Date

14Sep20

[name]
Biostatistician
Director, Product Development Strategy, NAMSA

[name]

Digitally signed by [name]
DN: cn=[name], o=NAMSA,
ou=C&C,
email=[contact],
c=US
Date: 2020.09.14 13:44:32 -05'00'

Table of Contents

1. Introduction	3
2. Abbreviations	3
3. Study Objectives	3
3.1. Primary Objective	3
3.2. Hypothesis	4
3.3. Primary Endpoint	Error! Bookmark not defined.
3.4. Secondary Objective	5
3.5. Secondary Endpoints	5
3.6. Ancillary Endpoints	9
4. Study Design	10
4.1. Sample Size	10
4.2. Randomization	10
4.3. Blinding	11
4.4. Study Assessments and Missing Data	11
4.5. Analysis Populations	11
4.6. Interim Analyses	Error! Bookmark not defined.
5. Methods	12
5.1. General Considerations	12
5.1.1. Descriptive Statistics	12
5.2. P-Values	12
6. References	12
7. Appendix 1 - LED Calculation	14
8. Appendix 2 – Statistical Tables	16

1.Introduction

The purpose of this statistical analysis plan is to describe the methods that will be used to analyze and report the clinical utility of Personal KinetiGraph movement recording system data in the clinical management of Parkinson’s disease (PD) using objective measurement and target ranges in neurology and movement disorders clinics in the U.S.

Subsequent versions of this analysis plan will document and describe any such changes. This plan is based on the protocol Version 1.0, dated June 6, 2019.

Prior to the planned protocol interim analysis, Global Kinetics notified all sites that enrollment was closed as of February 27, 2020. The contexts of this analysis plan will therefore reflect an adapted plan for all subjects enrolled prior to the notification of enrollment closure followed through the primary endpoint.

2.Abbreviations

- BKS: Bradykinesia Scores
- CGI-I: Clinician Global Impression of Improvement
- DKS: Dyskinesia Scores
- HCU: Healthcare resource utilization
- MDS: Movement Disorder Specialists
- PD: Parkinson’s Disease
- PDQ-39: Parkinson’s Disease Questionnaire - 39
- PGI-I: Patient Global Impression of Improvement
- PKG: Personal KinetiGraph
- MDS-UPDRS: Movement Disorder Specialist Unified Parkinson’s Disease Rating Scale

3.Study Objectives

3.1. Primary Objective

This is a randomized controlled trial (RCT) to evaluate treating uncontrolled patients with Parkinson’s Disease (PwP) to a target range established by published expert opinion. The study aims to evaluate clinical patient outcomes, quality of life measures and health care utilization of those patients specifically treated to a target range when using the PKG data in the clinical management of Parkinson’s disease (PD) in routine clinical care (treatment group) compared to those managed with medical history and clinical evaluation alone (control group) performed by a neurologist experienced in PD management. Both groups will be recommended to undergo medication changes until they reach a “controlled state” that is determined by either the clinician using standard of

care (SOC) (PKG- Group) or using PKG based targets and SOC assessments (PKG+ Group). For subjects in the treatment arm (PKG+ Group) the references will be according to the following table for purposes of analysis using PKG scores. Subjects will either be considered bradykinetic (BKS scores exceed targets; BKS >25) or Dyskinetic (DKS scores exceed targets; DKS >9):

	Target Range
Bradykinesia Score (BKS)	Median BKS 23-25
Dyskinesia Score (DKS)	Median DKS 7-9

The main objective of this study is to evaluate whether PwP who are managed with the aid of objective measurement and use of target ranges have improved PD symptoms and outcomes as compared to individuals treated using only standard of care (medical history, neurological examination).

3.2. Hypothesis & Primary Endpoint

Primary Endpoint: The change in MDS-UPDRS Total score at 4 months from baseline defined as sections I, II, III and IV in PwP. The endpoint will be compared between those who are treated with standard of care and PKG data (PKG+ Group) and those who are treated per standard of care alone (PKG- Group).

The primary endpoint of change in total MDS-UPDRS at 4 months will be compared between the treatment group (PKG+ Group) and the control group (PKG- Group) based on a two-sample t-test. In the event normality assumptions are violated, a non-parametric analog will be used. A difference between groups of 5 points is assumed for the change in total MDS-UPDRS as well as a standard deviation of 13 based on historical data. With these assumptions, a sample size of 280 evaluable subjects will provide approximately 83% power for the statistical hypothesis test for the primary endpoint. To account for attrition of up to 20%, a total enrollment of 350 subjects is planned. Enrollment was stopped in the study at 41 subjects enrolled. These 41 subjects will be followed through the 4-month endpoint and will be analyzed.

The difference in the primary endpoint between randomized groups will be compared with a two-sample t-test of means at the 1-sided alpha of 0.025 (equivalent to a two-sided 0.05 alpha level). In the event normality assumptions are violated, a non-parametric analog will be used.

The primary analysis will be based on the intent-to-treat (ITT) population defined as all randomized subjects analyzed according to the treatment group assigned. Except where otherwise specified, the following general principles apply to the planned statistical analyses. All statistical analyses will be conducted using SAS version 9.4 or later (SAS

Institute Inc., Cary, NC) or other widely-accepted statistical or graphical software as required. Continuous variables will be summarized with mean, standard deviation, median, max, min, and number of evaluable observations. Categorical variables will be summarized with frequency and percentages. Confidence intervals may be presented where appropriate using the t-distribution for continuous variables and Clopper-Pearson Exact method for categorical variables. Unless otherwise specified, statistical analyses will be performed using a one-sided 0.025 alpha level.

An additional analysis will be conducted due to impacts from COVID-19 for the primary endpoint. This will include looking at instances where a partial UPDRS Part III was collected due to restrictions when conducting a telehealth video visit.

Subgroup Analysis of Primary Endpoint

Subgroup analyses will be conducted to examine the possible influence of baseline characteristics on the primary outcome. Subgroups of interest may include but are not limited to:

- Duration of disease – defined by years of disease (Date of Visit 1 - Year of PD Diagnosis)
- Stage of PD - defined by Hoehn & Yahr (1-5) at Visit 1
- History of fluctuation – defined by patient wearing off in last 30 days at Visit 1
- Gender
- Age – defined by Date of Visit - DOB
- Controlled PD at Baseline Visit in PKG+ and PKG- groups as defined by the PKG for both groups.
- Uncontrolled PD at Baseline Visit in PKG+ and PKG- groups as defined by the PKG for both groups.

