4.1. Sample Size

Based on the original planned sample size, approximately 350 subjects were to be consented to provide an estimated 280 subjects followed through the 4-Month follow-up period (assuming 20% attrition). However, enrollment was stopped in the study at 41 subjects enrolled prior to any protocol defined interim analysis milestones being achieved. These 41 subjects will be followed through the 4-month endpoint and will be analyzed.

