5.2. P-Values

Unless otherwise specified, statistical analyses will be performed using a two-sided hypothesis test at the overall 5% level of significance. P-values will be rounded to three decimal places. If a p-value is less than 0.001 it will be reported as "< 0.001." If a p-value is greater than 0.999 it will be reported as "> 0.999."

6. References

- ICH Guidelines. E9: *Statistical Principles for Clinical Trials* <http://www.ich.org/ich5e.html>.
- Adaptive Designs for Clinical Trials of Drugs and Biologics Guidance for Industry November 2019; <https://www.fda.gov/regulatory-information/search-fda-guidance-documents/adaptive-design-clinical-trials-drugs-and-biologics-guidance-industry>

7. Appendix 1 - LED Calculation

LED Used for Parkinson's Studies- 28Jan2020

Reference Tomlinson article Table 2 or order in calculating the LED.

Medication	Conversion Factor (mg)	
Levodopa (immediate release)	X 1	
Levodopa CR (controlled release)	X 0.75	
Levodopa ER (extended release) "Rytary"	X 0.5	
Entacapone (or Stalevo™)	LD x 0.33	
Duodopa™	X 1.11	"When entering dose, consider total mg infused per day"
Pramiprexole	X 100	
Ropinirole	X 20	
Rotigotine	X 30	
Selegiline (oral)	X 10	
Selegiline (sublingual)	X 80	
Cabergoline	X 100	
Rasagiline	X 100	
Amantadine	X 1	

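### SAP 3.2 still rests the primary test on 83% power at 280 evaluable, gives no power or precision for the 41 subjects to be analysed, and does not require the between-group difference with its confidence interval

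*SAP*

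**What the plan says.** The SAP Introduction says that enrolment closed on February 27, 2020, before the planned interim analysis, and that the document is an adapted plan for those already enrolled. Section 3.2 then carries the protocol's justification: "A difference between groups of 5 points is assumed for the change in total MDS-UPDRS as well as a standard deviation of 13", with 280 evaluable subjects giving approximately 83% power and 350 enrolled to allow for 20% attrition. It adds "Enrollment was stopped in the study at 41 subjects enrolled". Section 4.1 puts the 350/280 target in the past tense and continues: "These 41 subjects will be followed through the 4-month endpoint and will be analyzed".

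The primary test remains a two-sample t-test at one-sided 0.025, which section 3.2 equates with two-sided 0.05. On departures from normality it says: "In the event normality assumptions are violated, a non-parametric analog will be used". The analog is not named.

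On reporting, sections 3.2 and 5.1.1 require mean, SD, median, range and number of evaluable observations for continuous variables. Intervals are discretionary: "Confidence intervals may be presented where appropriate using the t-distribution". Section 4.4 rules out imputation and allows for MDS-UPDRS Part III being partly collected or not collected at baseline and/or 4 months.

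**The concern.** The SAP was written when the cohort size was known, yet the only operating characteristic in its primary section belongs to a trial about seven times larger (280/41 = 6.8). A reader who meets a non-significant p-value beside a statement of 83% power could take the result as informative evidence against a 5-point benefit. At 41 subjects it would not be.

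At this size the useful result is the estimated difference and its interval, because the interval shows how wide a range of effects remains compatible with the data. The SAP leaves that interval optional. If normality is judged to fail, the specified primary analysis becomes a non-parametric test, and nothing then requires any between-group estimate in MDS-UPDRS points.

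**Working it through.** **Inputs.** Difference 5, SD 13 and one-sided alpha 0.025 (SAP 3.2). Planned size 280 evaluable, 350 enrolled, 20% attrition (SAP 3.2). Cohort 41 (SAP 3.2 and 4.1). Allocation 1:1 (SAP 4.2).

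**Assumptions.** The actual split is not given, so I take 20 vs 21. As a lower case I apply the planned 20% attrition to 41: 41 × 0.80 = 32.8, about 33, taken as 16 vs 17.

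**Formulas.**
- SE = SD × √(1/n1 + 1/n2)
- Noncentrality = difference / SE
- Power = P(noncentral t with n1 + n2 − 2 df exceeds t(0.975, df))
- 95% half-width = t(0.975, df) × SE, with SD set at 13

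**The plan's own figures.** The attrition step reproduces: 280 / (1 − 0.20) = 350. The 83% does not. With 140 per arm, SE = 13 × √(2/140) = 1.554 and noncentrality = 5 / 1.554 = 3.218. Power is 89.4% at the stated alpha (89.6% by the normal approximation). A figure of 83.2% appears only if 0.025 is halved again to one-sided 0.0125. That is a separate matter. The calculations below use the alpha that the SAP states.

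**The adapted cohort.**

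| | 140 vs 140 | 20 vs 21 | 16 vs 17 |
|---|---|---|---|
| SE (points) | 1.55 | 4.06 | 4.53 |
| Noncentrality at 5 points | 3.22 | 1.23 | 1.10 |
| t(0.975, df) | 1.969 | 2.023 | 2.040 |
| Power for 5 points | 89.4% | 22.4% | 18.7% |
| 95% half-width (points) | 3.1 | 8.2 | 9.2 |
| Difference with 80% power (points) | – | 11.7 | 13.1 |

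With 41 evaluable and an observed SD of 13, an observed difference of exactly 5 points would have a 95% interval of 5 ± 8.2, that is −3.2 to 13.2.

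**Sensitivity with 41 evaluable.**
- An 18 vs 23 split gives 22.1%.
- Assumed SDs of 8, 10 and 15 give 49.6%, 34.5% and 17.9%.
- The two-sided 5% level in SAP 5.2 has the same critical value as one-sided 0.025, so the power is effectively unchanged.
- At one-sided 0.0125, the level that matches the printed 83%, power would be 14.7%.

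**Estimates that reach significance.** I simulated 400,000 trials at 20 vs 21 with SD 13. If the true difference is 5, the estimates that are significant in favour of PKG+ average 10.3 points, about twice the truth. At true differences of 8 and 12 the ratio is about 1.4 and 1.1.

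**The case against.** The strongest defence is that the SAP is open about the shortfall. The Introduction, section 3.2 and section 4.1 all disclose the closure, and 4.1 presents 350/280 as what had been intended. Keeping the prespecified test is legitimate: low power does not invalidate it or inflate its type I error, and the sample size can no longer change. All of this stands. It answers a charge of concealment or of an invalid test, and the documents support neither.

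A reader might also infer that the primary output is a bare p-value. That goes too far. Means, SDs and numbers evaluable must be reported whether or not normality holds, and from arm-level summaries the difference and a t-based interval can be derived. What is missing is a requirement to report them as the result.

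A reader might further infer that the final tables will contain no interval. Appendix 2, which holds the statistical tables, is an attachment that was not available, and its shells may include one. The text that governs the analysis leaves intervals optional.

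Finally, a reader might see a superiority verdict here, or conclude that any significant result would be doubled. The SAP does not use the word superiority and sets no success criterion; it keeps a one-sided test of a between-group difference. The doubling holds only if the true difference is 5, and it shrinks as the true effect grows.

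**Conclusion.** The point holds as a reporting and justification gap in the primary analysis, and it should be fixed. It does not show the planned test to be wrong, so a must-fix rating would be too strong.

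Section 3.2 supports the primary test with figures for a trial that will not take place and gives none for the one that will. Under the SAP's own difference, SD and alpha, power for 5 points is about 22% if all 41 are evaluable and about 19% if 33 are, with half-widths of about 8.2 and 9.2 points. At SD 13 the 22% is effectively a ceiling, because it assumes full follow-up and a near-equal split, while section 4.4 rules out imputation and foresees missing Part III data. A smaller SD would raise it, but even an assumed SD of 8 gives only about 50%.

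These figures are for the t-test and rest on the assumed split and attrition. The between-group difference and its interval, the most informative result at this size, are left to discretion, and no between-group estimate is required if the non-parametric route is taken.

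**What to change.** 1. In SAP 3.2, mark the 280, 350 and 83% figures as belonging to the original plan only.
2. In SAP 3.2 or 4.1, state the power and expected 95% half-width for the evaluable cohort: about 22% and 8.2 points with 41, and about 19% and 9.2 points with 33, with the assumed split and SD. Update these when the evaluable number by arm is known.
3. In SAP 3.2, require the PKG+ minus PKG- difference in mean change with its two-sided 95% confidence interval as the main primary result, whether or not normality holds. Name the non-parametric test and make it a sensitivity analysis.
4. Check that the Appendix 2 tables show this difference and interval.

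A sentence saying that a non-significant result is not evidence of no benefit would help but is optional.

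The cost is SAP wording only, plus a printed power far less favourable than the one there now. No new data, design change or change of test level is needed.
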